### 7.5 NCI GUIDANCE FOR REPORTING EXPEDITED ADVERSE EVENTS FOR MULTI-CENTER TRIALS

The site PI must immediately report to the coordinating center PI any serious adverse event, whether or not considered drug related, including those listed in the protocol or investigator brochure and must include an assessment of whether there is a reasonable possibility that the drug caused the event within 24 hours of PI awareness of the event. The Site PI must also report any protocol deviations to the coordinating center PI within 7 days of PI awareness. Participating centers must also submit the report to their IRB in accordance with their institutional policies.

Participating centers must also submit the report to their IRB in accordance with their institutional policies. The CCR problem report form will be used for this purpose (Appendix [12.9](#)).

Occasionally NCI IRB or the PI may contact the reporter for additional information, clarification, or current status of the subject for whom an adverse event was reported.

### 7.6 REPORTING TO THE STUDY DRUG MANUFACTURERS

The NCI Coordinating Center will forward all SAE reports to the NCI IRB and GSK Pharmaceuticals Clinical Safety and Epidemiology Department (CS&E).

GSK Pharmaceuticals Clinical Safety and Epidemiology Department (CS&E).

[contact]

**SAEs will be forwarded to GSK Pharmaceuticals Clinical Safety and Epidemiology Department (CS&E) in accordance with the following:**

All serious adverse events should be reported to GSK Pharmaceuticals Clinical Safety and Epidemiology Department (CS&E) within 24 hours. In the event of an SAE, the investigator should refer to the Pharmacovigilance section of the contract for reporting procedures. In brief:

**The Investigator/Sponsor may report serious adverse drug reactions (SADRs) using either:**

An ADEERS form (Adverse Event Expedited Reporting System) available at  
<http://ctep.cancer.gov/reporting/adeers.html>

OR

A MedWatch form available at <http://www.fda.gov/medwatch/>

Occasionally the coordinating center may contact the reporter for additional information, clarification, or current status of the subject for whom an adverse event was reported.

## **7.7 GUIDELINES & PROCEDURES FOR REPORTING VIOLATIONS, DEVIATIONS AND UNANTICIPATED PROBLEMS**

Neither the FDA nor the ICH GCP guidelines define the terms “protocol violation” or “protocol deviation.” The definition is often left to the Lead Institution IRB. Accordingly, since NCI, Center for Cancer Research is the Coordinating Center and the Protocol Chair must adhere to those policies set by the NCI IRB, the definitions for unanticipated problem and protocol deviation as described by the NCI IRB will be applied for reporting purposes for all institutions participating in the NCI Center for Cancer Research Multi-center Project.

Definitions are listed in section **7.2**

Protocol Deviations or Unanticipated problems occurring at a participating institution will be submitted to that institution’s own IRB in accordance with local policies and procedures. However, the participating institution must submit a report to the NCI CCR Coordinating Center even in instances where the local IRB does not require a report.

Deviations or Unanticipated problems must be submitted to the NCI CCR Coordinating Center within 7 calendar days after the original submission to the IRB, or after becoming aware of the event (if not reportable to the local IRB), or upon receipt of notification from the NCI CCR Coordinating Center. When Deviations or Unanticipated Problems are reported to NCI CCR, but, the local IRB does not require a report, the report that is submitted to the NCI CCR Coordinating Center must be accompanied by a formal memo explaining the local policy and the rationale for not reporting the event to the local IRB.

Deviation or Unanticipated problem Reports and any accompanying documentation (to include the local IRB acknowledgement of the event when applicable) are to be submitted to the NCI CCR Coordinating Center using the problem report form in section **12.9**.

NCI Center for Cancer Research Coordinating Center: Upon receipt of the deviation/unanticipated problem report from the participating institution, the NCI CCR

Coordinating Center will submit the report to the lead Protocol Chair for review. Subsequently, the participating institution's IRB deviation/unanticipated problem report will be submitted to the NCI IRB for review.

## **7.8 DATA AND SAFETY MONITORING PLAN**

### **7.8.1 Principal Investigator/Research Team**

The clinical research team will have a teleconference every other week when patients are being actively treated on the trial to discuss each patient. Decisions about dose level enrollment and dose escalation if applicable will be made based on the toxicity data from prior patients.

All data will be collected in a timely manner and reviewed by the principal investigator or a lead associate investigator. Adverse events will be reported as required above. Any safety concerns, new information that might affect either the ethical and or scientific conduct of the trial, or protocol deviations will be immediately reported to the IRB using iRIS.

The principal investigator will review adverse event and response data on each patient to ensure safety and data accuracy. The principal investigator will personally conduct or supervise the investigation and provide appropriate delegation of responsibilities to other members of the research staff.

### **7.8.2 NCI Coordinating Center Monitoring Plan**

Data will be reviewed by the study coordinator at the NCI Center for Cancer Research, who will check for missing data, non-compliance, and adverse events. Missing data will be requested from participating sites. The study coordinator and PI meet weekly and discuss the data as needed. The PI and study coordinator will ensure that all non-compliance and unanticipated problems are reported to the NCI IRB in accordance with reporting requirements.

## **8 STATISTICAL CONSIDERATIONS**

The primary goal of this trial will be to assess time to progression, defined as progressive disease, toxicity at a level of severity that precludes the patient continuing on the protocol, or death. Patients will be accrued up to a maximum sample size of 50. Safety monitoring of failure time will be done as follows. Every 2 months, the data from each patient will consist of the time to failure. We define  $T_i$  to be the Time to Progression for the  $i$  th patient

parameterized via a median parameter such that  $T_i | Q_E \sim \text{Exp}(Q_E)$  and  $\text{Median}(T_i) = Q_E$ . We assume that  $Q_E$  has prior distribution  $\text{Inverse Gamma}(a_E, b_E)$  with expectation  $b_E / (a_E - 1)$ . Thus, for each treatment the posterior distribution of  $Q_E | \text{Data}$  is

$\text{Inverse Gamma}(a_E + m_E, b_E + \ln(2) \sum T_i)$  (where  $m_E$  is the number of events in the trial). *A*

*priori*, it is assumed that the median PFS time  $Q_E$  follows an inverse gamma distribution with shape parameter= 2 and scale parameter =17.6761. This prior distribution has median of 10.5 months. The historical median PFS time is represented by  $Q_S$ . In addition,  $Q_S$  is assumed to follow an inverse gamma distribution with shape parameter= 2000 and scale parameter =21000. (This prior also has median of 10.5 months).

The trial will be stopped early if, based on the current data,  $\Pr(Q_E > Q_S + 3.5 | \text{data}) < 0.065$ . That is, the trial will be stopped early if, it is very unlikely that the median time to progression with the experimental therapy (temozolomide and lapatinib) is less than the historical median time to progression for the standard treatment as described in the literature. The rule will be applied every 2 months, with the probability criterion recomputed based on the most recent data available at that time. Based on an anticipated accrual rate of 2.5 patients per month, the trial is expected to complete accrual in 40 months.

To obtain operating characteristics of the early stopping rule, the trial was simulated under three scenarios, which we have summarized in the Table below. The design's operating characteristics are as follows. Each entry in the table is the mean from 2000 simulated trials:

**Table Operating Characteristics.** Maximum sample size 50

Case	Median Time to Progression	Pr(Stop Early)	# Patients (25%,75%)
Scenario 1	2.0	1	16.435 ( 13, 19 )
Scenario 2	7.0	0.896	36.694 ( 27, 50 )
Scenario 3	10.5	0.173	47.354 ( 50, 50 )
Scenario 4	14.0	0.034	49.054 ( 50, 50 )

We also summarize the median lower and median upper credible intervals for this trial on an assumption of that the data follows an exponential distribution (with median survivals summarized in the Table below). To calculate the expected lower and expected upper credible intervals we simulated progression free survival data (1000 simulations) from exponentially distributed data and assuming observations without events were censored at 48 months (40 months of accrual and 8 months of additional follow-up). For each simulation we recorded the lower (1st decile) and upper (9th decile) credible sets from the posterior distribution of the median PFS parameter. At the end of the simulation we then calculated and recorded below the median 1st decile and median 9th deciles from the vector of recorded deciles obtained from our simulation.

True Median Survival	Median 1 st decile and Median 9 th decile	Credible Limits
10.5 Months		(8.72, 12.50)
14 Months		(11.52, 16.66)

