## **1 INTRODUCTION**

### **1.1 STUDY OBJECTIVES**

#### **1.1.1 Primary Objective**

To determine the efficacy of the combination of temozolomide and lapatinib in recurrent brain ependymoma and anaplastic ependymoma as measured by median progression-free survival.

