## **6.2 RESPONSE CRITERIA**

6.2.1 The primary endpoint is median progression-free survival. A combination of the neurological examination and MRI brain scan will be used to define progression. Due to improvements in neuroimaging and the fact that tumor growth in certain regions of the CNS is without immediate neurologic signs and symptoms, greater reliance is placed on neuroimaging to define progression.

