6.2.3 Response Criteria

6.2.3.1 **Stable/No Progression:** No evidence of new measurable lesions on MR imaging. The designation of Stable/No Progression requires a minimum of 12 weeks duration. All measurable and evaluable sites must be assessed using the same techniques as baseline.

6.2.3.2 **Partial response:**  $\geq 50\%$  reduction in the sum of products of all measurable lesions over baseline sum observed using the same techniques as baseline. The patient must be on a stable or decreased dose of corticosteroids to be evaluable for response.

6.2.3.3 **Complete response:** Complete resolution of all lesions. The patient cannot be on any corticosteroids with the exception of adrenal replacement doses.

6.2.3.4 **Progression:** 25% increase in the sum of products of all measurable lesions over smallest sum observed (over baseline if no decrease) using the same techniques as baseline, OR clear worsening of any evaluable disease, OR appearance of any new lesion/site, OR failure to return for evaluation due to death or deteriorating condition (unless clearly unrelated to this cancer).

6.2.3.5 **Unknown:** Progression has not been documented and one or more measurable or evaluable sites have not been assessed.

6.2.4 **Neurologic Function Score:** This method of neurologic evaluation notes the presence or absence of neurologic symptoms. This examination should coincide with objective measurement in tumor size.

0	No neurologic symptoms
1	Minor neurologic symptoms
2	Moderate neurologic symptoms – fully active
3	Moderate neurologic symptoms – less than fully active
4	Severe neurologic symptoms

- 6.2.5 **Performance Status:** Patients will be graded according to Karnofsky Performance Status (KPS)
- 6.2.6 **Time to Treatment Failure:** From date of registration to the date of first observation of progressive disease, non-reversible neurologic progression or permanently increased steroid requirement (applies to stable disease only), death due to any cause, or early discontinuation of treatment.
- 6.2.7 **Survival:** From date of registration to date of death due to any cause
- 6.2.8 **NOTE: Steroids:** Steroid dosage will be carefully monitored and recorded during each course of therapy and steroid dosage changes will be considered before response determinations are made.

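### Section 8 counts protocol-ending toxicity as an event in the primary time but labels its median as median PFS, so a PFS reported from it can only be equal to or below progression-or-death PFS

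*Combined protocol and SAP*

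**What the plan says.** The primary objective (1.1.1) is efficacy "in recurrent brain ependymoma and anaplastic ependymoma as measured by median progression-free survival", and 6.2.1 repeats this: "The primary endpoint is median progression-free survival". Section 6.2.1 bases progression on neurological examination and MRI. Section 6.2.3.4 lists lesion growth, "OR clear worsening of any evaluable disease, OR appearance of any new lesion/site", and failure to return because of death or deterioration. Toxicity does not appear. Section 6.2 never defines PFS as a time-to-event variable.

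Section 8 supplies the only event set for the primary time. The goal is to "assess time to progression, defined as progressive disease, toxicity at a level of severity that precludes the patient continuing on the protocol, or death". The next step is introduced with "Safety monitoring of failure time will be done as follows", and the per-patient data are times to failure. The median of this time is the parameter Q_E. Section 8 then says "it is assumed that the median PFS time" has an inverse gamma prior, and "The historical median PFS time is represented by" Q_S. The credible limits at the end of the design description are also labelled as those of the median PFS parameter.

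The composite is not Time to Treatment Failure (6.2.6) either. That runs "From date of registration to the date of first observation of progressive disease, non-reversible neurologic progression or permanently increased steroid requirement", and also counts death and any early discontinuation of treatment, which is a broader set.

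**The concern.** One variable carries three names in Section 8: time to progression, failure time and PFS. Its event set fits the second name but not the third. An analyst who follows Section 8 literally would end a patient's time at a toxicity stop and publish the resulting median as median PFS. A reader of the result who knows only the label would take it as time to progression or death.

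The trial is single-arm and is judged against a historical median, so the meaning of the primary median is the main thing at stake. Accrual is closed (2.3), so what can still be affected is the reported result. The event set behind the 10.5-month historical median is not stated. The literature benchmark in 1.2.2 is a median time to progression of 9.9 months, with no mention of toxicity. Neither version of T_i is therefore shown to match the comparator.

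**Working it through.** **Inputs from Section 8.** n = 50; prior for Q_E Inverse Gamma(2, 17.6761); posterior Inverse Gamma(2 + m, 17.6761 + ln 2 × ΣT), with m events; all times censored at 48 months; printed 10%–90% limits (8.72, 12.50) at a true median of 10.5 months and (11.52, 16.66) at 14.

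**Assumed, because the documents give no figure.** f = share of first events that are toxicity stops.

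**1. Reproduce the printed limits.** Simulate 50 exponential times, censor at 48 months, and take the median over trials of the 10% and 90% posterior quantiles (20,000 trials). The result is 8.74–12.57 at 10.5 months and 11.54–16.77 at 14. Runs of 1000 trials, the protocol's number, range over 8.64–8.88 and 12.39–12.78 at 10.5, and 11.37–11.69 and 16.50–17.00 at 14. The printed limits lie inside these ranges. They come from a plain exponential with no toxicity process.

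**2. Direction.** For each patient, the time to progression, toxicity stop or death is at most the time to progression or death. So ΣT falls or is unchanged, m rises or is unchanged, and the posterior for the median can only move down or stay. This needs no assumption about f or about dependence.

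**3. Size, independent exponential hazards.** Let the progression-or-death hazard be λ = ln 2 / M. If toxicity stops are a share f of first events, the total hazard is λ / (1 − f), so the composite median is M × (1 − f). For M = 14:

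| f | Composite median (months) | Median 10%–90% limits | Chance that the upper limit is below 14 |
|---|---|---|---|
| 0 | 14.0 | 11.5–16.7 | 0.12 |
| 5% | 14 × 0.95 = 13.3 | 11.0–15.9 | 0.19 |
| 10% | 14 × 0.90 = 12.6 | 10.4–15.1 | 0.31 |
| 20% | 14 × 0.80 = 11.2 | 9.3–13.4 | 0.62 |

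Among 50 patients these shares are about 2, 5 and 10 toxicity events. Repeat runs agree to about 0.01 in the last column.

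**4. Size under dependence, f = 10% and 20%, M = 14.**
- Stops mainly in patients who would progress early (Gaussian copula, correlation +0.5): limits 10.9–15.8 and 10.2–14.7. The shift is smaller.
- Stops mainly in patients who would progress late (correlation −0.3): 10.1–14.6 and 8.8–12.7. The shift is larger.
- All toxicity stops in the first 6 months: 10.3–14.9 and 9.1–13.2.

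**5. Precision of progression-or-death PFS, M = 14.**
- Every patient followed to 48 months, as Section 8 assumes: about 45 events, limits 11.5–16.7.
- Uniform entry over 40 months plus 8 months' follow-up: about 35 events, limits 11.3–17.2.
- 48-month case, but censored at the toxicity stop because later disease status is missing: 41.8 events and 11.4–16.9 at f = 10%; 38.0 events and 11.3–17.0 at f = 20%. This is unbiased only if toxicity stops are independent of progression.

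**The case against.** Section 8 contains no explicit final-analysis statement. The model for T_i is introduced as safety monitoring, where counting toxicity may be deliberate, and the opening sentence of Section 8 discloses the event set to anyone who reads it. This stands in part. It makes the link to the reported result an inference. But the composite is stated as the primary goal, and no other text gives an event set for PFS.

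The size is unsupported: no toxicity-stop rate is given, both drugs have reduced dose levels and holds before a stop (3.3), and patients stopped for cardiac events remain in the study (3.3.1.4.1.4), so the toxicity clause could be read narrowly. This stands. At f = 5% the shift is 14 − 13.3 = 0.7 month, and it may be zero.

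The bias runs against the treatment, so it cannot create a false positive. That is correct, but it can hide a real gain, and it changes what the primary number means.

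Following patients past a toxicity stop brings in progression-free time on later regimens. The protocol expects such treatment: follow-up records treatment regimens (3.7.9.2), and the laboratory summaries in Section 8 refer to later anti-tumour therapy. This stands, and the fix has to deal with it.

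A reader might also infer that a full 3.5-month improvement would be hidden. That is only 14 × 0.75 = 10.5 with f set at 25% and hazards independent; nothing in the documents supports 25%, and under positive dependence (+0.5) the limits at that share are 9.8–14.1 and still contain 14.

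**Conclusion.** The mismatch is explicit, and no other passage resolves it. Its direction is certain: if the Section 8 posterior is the basis of the reported primary result, the value labelled median PFS is at or below the progression-or-death median, and strictly affected only when some patient has a toxicity stop first. Its size is conditional on f. For a true median of 14 months with independent exponential hazards, the analysed median is lower by 0.7, 1.4 and 2.8 months at f = 5%, 10% and 20%, with less shift if stops fall mainly in early progressors and more if in late progressors.

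Two stronger readings are not supported. The printed credible limits are not wrong; they reproduce. Nor do the documents show that the interim rule is wrong to count toxicity; that is a design choice, and only its label needs correcting. The point should be fixed before the primary result is reported.

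**What to change.** For the reported primary median PFS and its credible limits, define T_i as time from registration to first progression per 6.2.3.4 or death from any cause. A toxicity stop is not itself an event.

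- Report the Section 8 composite beside it, named time to progression, protocol-precluding toxicity or death. Say which stops count and that it differs from 6.2.6.
- Report both results whatever they show, and state when the change was made relative to data review. A change after accrual that can only lengthen the median could otherwise look selective.
- State how patients who start new anti-tumour therapy before progression are handled (censored at its start or followed through it), with the other handling as a sensitivity analysis.
- Where disease status was not obtained after a toxicity stop, censor at the last adequate disease assessment. Section 3.7.9.2 and study calendar footnote 5 ask for quarterly disease-status updates without naming MRI, so their wording should be reconciled with 3.7.9.1. New wording cannot recover scans that were not taken.
- If the interim rule keeps the toxicity-inclusive time, call it failure time and not PFS. Taking toxicity out would remove that rule's only toxicity input, so this fix does not ask for it.

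The cost is wording and one extra summary. Precision should be quoted as in step 5: the protocol's own limits hold only with 48 months of follow-up for every patient, are wider with staggered entry, and are somewhat wider again if patients are censored at toxicity stops.

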Currently, the standard therapy for newly diagnosed low-grade ependymoma includes total surgical excision followed by radiation therapy. Complete surgical resection is often not possible because of the location of the tumor and the concern for damage to surrounding eloquent brain during surgery. The situation is even more critical for patients with anaplastic ependymomas because of the higher proliferative rate and greater propensity for tumor infiltration into surrounding normal brain, preventing any possibility of complete tumor removal by surgery. For patients with the more aggressive anaplastic ependymoma, chemotherapy is often administered either before or after the radiation in the hope that infiltrating tumor cells will be eliminated. Unfortunately, even for patients with low-grade ependymoma, survival can be poor when the tumor is not totally surgically resected.

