### 1.2.2 Treatment of recurrent ependymoma

There have only been a limited number of reports describing chemotherapy treatments for patients with recurrent ependymoma, either low grade or anaplastic. As a consequence, optimal therapy for this group remains unknown. Traditionally, combination chemotherapy regimens have been used, often containing either carboplatin or cisplatin. Many of these treatment programs were associated with a high incidence of moderate to severe toxicity.

A recent publication by Brandes and colleagues underscores some of the limitations in determining the optimal treatment for recurrent disease(Brandes, Cavallo et al. 2005). They report on the treatment of 28 adults who had recurrent ependymoma (n = 17) or anaplastic ependymoma (n = 11) after initial treatment with surgery and radiation. Half of the patients had undergone multiple tumor resections. A wide variety of regimens were used ranging from single agent temozolomide to the “8 in 1” regimen that combines 8 different chemotherapy agents. For their analyses, they looked at the composite group as well as a comparison of patients treated with or without cisplatin. No overall differences were noted based on the use of cisplatin. Furthermore, the overall objective response rate was 20% (CR and PR). The 12 month progression free survival rate was 44% (95% CI, 29-68%). The median time to progression was 9.9 months. These data provide a benchmark for subsequent clinical trials evaluating treatments for adults with recurrent ependymomas.

There have been anecdotal reports of response of ependymoma to temozolomide. The study by Brandes included 4 patients who received this either as single agent (n = 3) or in combination with cisplatin (n = 1)(Brandes, Cavallo et al. 2005). All patients were reported to have stable disease as their best response. A single case report describes a patient with recurrent anaplastic ependymoma with a greater than 10 year response to temozolomide therapy(Rehman, Brock et al. 2006). There is no published literature on the use of signal transduction modulating agents, save for a recent phase I study of the farnesyltransferase inhibitor lonafarnib in patients with recurrent primary pediatric brain tumors(Kieran, Packer et al. 2007). A single patient with a recurrent ependymoma did achieve stable disease with this regimen.

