## **2 ELIGIBILITY ASSESSMENT AND ENROLLMENT**

### **2.1 ELIGIBILITY CRITERIA**

#### **2.1.1 Inclusion Criteria**

- 2.1.1.1** Histologically proven ependymoma or anaplastic ependymoma. There must be pathologic or imaging confirmation of tumor progression or regrowth. The patient's histologic diagnosis must be confirmed on Central Pathology Review prior to registration Step 2.
- 2.1.1.2** The patient must have at least 1 block of tissue available or 15 unstained slides at a minimum, for central pathology review and molecular profiling of the tissue sample.
- 2.1.1.3** History and physical examination, including neurologic examination, within 2 weeks prior to registration.

- 2.1.1.4** Patients must be able to undergo brain or spine MRI scans with intravenous gadolinium, based on tumor location(s) within 14 days prior to registration.
- 2.1.1.5** Patients must be on a steroid dose that has been stable or decreasing for at least 5 days. If the steroid dose is increased between the date of imaging and registration, a new baseline MRI is required.
- 2.1.1.6** Karnofsky performance status  $\geq 70$
- 2.1.1.7** Age  $\geq 18$
- 2.1.1.8** CBC/differential obtained within 14 days prior to registration, with adequate bone marrow function defined as follows:
  - Absolute neutrophil count (ANC)  $\geq 1,500/\text{mm}^3$
  - Platelets  $\geq 100,000 \text{ cells/mm}^3$
  - Hemoglobin  $\geq 10.0 \text{ gm/dL}$  (Note: The use of transfusion or other intervention to achieve Hgb  $\geq 10.0$  is acceptable)
  - White blood cell count (WBC)  $\geq 3,000/\text{mcL}$
  - Adequate liver function within 14 days prior to registration, defined as follows: SGPT (ALT)  $< 2.5$  times the upper limit of normal, Bilirubin  $\leq 1.6 \text{ mg/dL}$
  - Adequate renal function within 14 days prior to registration, defined as follows: Creatinine  $< 1.7 \text{ mg/dL}$
- 2.1.1.9** Patients must have recovered from the toxic effects of prior therapy, and there must be a minimum time of:
  - 28 days from the administration of any investigational agent
  - 28 days from administration of prior cytotoxic therapy with the following exceptions:
    - 14 days from administration of vincristine
    - 42 days from administration of nitrosoureas
    - 21 days from administration of procarbazine
    - 7 days from administration of non-cytotoxic agents [e.g., interferon, tamoxifen, thalidomide, cis-retinoic acid, etc. (radiosensitizer does not count)].

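### Section 8 compares one pooled trial median with one historical median and takes no account of grade, so a grade mix unlike the benchmark's would be read as a treatment effect

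*Combined protocol and SAP*

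**What the plan says.** On the historical side, Section 8 states: "The historical median PFS time is represented by" one parameter, Q_S, with an inverse gamma prior (shape 2000, scale 21000) whose median is 10.5 months. It identifies the comparator only as "the historical median time to progression for the standard treatment as described in the literature". The trial side is also one parameter, Q_E, for all patients.

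Section 1.2.2 describes one benchmark series: "28 adults who had recurrent ependymoma (n = 17) or anaplastic ependymoma (n = 11) after initial treatment with surgery and radiation". For the pooled group it reports: "The median time to progression was 9.9 months". It gives no median by grade and adds: "These data provide a benchmark for subsequent clinical trials evaluating treatments for adults with recurrent ependymomas".

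Section 2.1.1.1 admits "Histologically proven ependymoma or anaplastic ependymoma", with no cap or stratum by grade. Histology must be confirmed by central review before registration Step 2, and Section 5.1.3.1 requires grade II or III features. Section 1.2.1 says of prognosis: "The situation is even more critical for patients with anaplastic ependymomas because of the higher proliferative rate". Section 8 contains no grade-specific or grade-adjusted analysis of PFS. Section 5.2 mentions grade only in connection with a future molecular classification.

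**The concern.** With a single arm, the efficacy reading is the distance between the trial's median and the historical one. That distance contains the drug effect and any difference in case mix. The protocol itself describes the anaplastic tumours as the more malignant and more aggressive of the two grades it enrols. If the trial's share of grade II differs from the benchmark's 61%, the pooled median moves even when the regimen does nothing, and the plan has no analysis that would show it.

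What is at stake is the interpretation of the primary result. A trial rich in grade II disease could look better than history, and one rich in anaplastic disease could look worse.

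**Working it through.** **Inputs from the documents.** Benchmark mix 17:11, so the grade II share is w0 = 17/28 = 0.607 (Section 1.2.2). Q_S ~ IG(2000, 21000), Q_E ~ IG(2, 17.6761), maximum 50 patients, looks every 2 months, stopping cut-off 0.065 (Section 8).

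**Assumptions, not in the documents.** A grade III to II hazard ratio (HR) for PFS of 1.5, 2 or 3; exponential times within grade; a 17:11 mix with a median of 10.5 months. If 9.9 months were used instead, every median below would scale by 9.9/10.5 = 0.943 and the proportional shifts would not change.

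**Step 1: the plan's own figures.** The two prior medians reproduce (10.53 and 10.50 months). The tabulated credible limits reproduce to about 1% when all patients are censored at 48 months: 8.75 to 12.60 against 8.72 to 12.50, and 11.52 to 16.72 against 11.52 to 16.66. The stopping table (0.896, 0.173, 0.034 at true medians of 7, 10.5 and 14 months) does not follow from the rule as written. With the 3.5-month margin, simulation gives 0.97 to 1.00, 0.56 to 0.71 and 0.19 to 0.25. With no margin it gives about 0.88, 0.17 and 0.03. That discrepancy is a separate matter, but it decides which stopping figures can be quoted here.

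**Step 2: medians by grade.** The pooled curve is S(t) = w·2^(−t/m_II) + (1−w)·2^(−t/m_III), with m_III = m_II/HR. Solve S(10.5) = 0.5 at w = 17/28.

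For HR 2, m_II = 14.0 and m_III = 7.0. Check: 0.607 × 2^(−0.75) + 0.393 × 2^(−1.5) = 0.361 + 0.139 = 0.500.

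**Step 3: move w with no treatment effect.**

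| HR | m_II / m_III | 40% grade II | 61% | 80% |
|---|---|---|---|---|
| 1.5 | 12.4 / 8.3 | 9.6 | 10.5 | 11.4 |
| 2 | 14.0 / 7.0 | 9.1 | 10.5 | 12.1 |
| 3 | 16.8 / 5.6 | 8.2 | 10.5 | 13.3 |

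The apparent effect of an inert regimen is therefore −0.9 to −2.3 months at 40% grade II and +0.9 to +2.8 months at 80%, against the 3.5-month margin written in Section 8.

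**Step 4: are 40% and 80% out of reach?** Treat the 28 benchmark patients and 50 trial patients as random draws from one population with share 0.607. The difference in observed shares has standard error √(0.2385/28 + 0.2385/50) = √0.01329 = 0.115. A 95% range is 60.7% ± 22.6 points, or 38% to 83%. Chance alone does not exclude either value; neither is a forecast.

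**Step 5: does standardisation recover the answer?** In simulated trials of 50 patients (HR 2, true benchmark-mix median 10.5), the pooled posterior median was 8.7, 9.2 and 12.2 months at 30%, 40% and 80% grade II. Fitting each grade separately and taking the median of (17/28)·S_II(t) + (11/28)·S_III(t) gave 10.3, 10.4 and 11.0.

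**The case against.** Several counter-arguments have force.

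- **Source of Q_S.** Section 8 does not tie Q_S to the 17:11 series, and 10.5 is not 9.9. A reader might infer that the comparator is known to be a 17:11 mix; the documents do not establish that. If Q_S came from elsewhere, its grade mix is simply undocumented, which leaves the comparison no better protected.
- **Effect size.** No hazard ratio for grade is given. Section 1.2.1 discusses newly diagnosed disease and resectability, not progression after recurrence. The direction is supported in words; the size is assumed.
- **Expected shift.** Section 1.2.1 says anaplastic tumours are more common in adults. A reader might infer that the trial will be richer in them than the benchmark. It does not follow, because the benchmark series is itself adult. The mix is uncontrolled; no departure is predicted.
- **Stopping rule.** A reader might infer that the shift would often kill an active regimen. With no margin, the version that approximates the plan's table, a regimen worth 14 months in the benchmark mix is stopped in only about 2 to 3%, 6 to 7% and 11% of simulated trials at 61%, 40% and 30% grade II (HR 2). The larger figures (24%, 44%, 58%) arise only with the written 3.5-month margin, which does not reproduce that table. For an inert regimen, stopping more often is not an error. Section 2.3 says accrual is closed, so the interim rule has little remaining force.
- **No success criterion.** Section 8 sets none, so looking active means only that the trial is not stopped and the posterior lies high.
- **Availability of grade.** Central review confirms WHO criteria, but no passage says grade is recorded as an analysis variable. That is likely, not stated.

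These points limit the size and certainty of the concern. They leave the gap itself: no PFS analysis can separate grade mix from treatment.

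**Conclusion.** The concern stands as a gap in interpretation with a cheap remedy. Section 8 sets a pooled median from an uncontrolled grade mix against a single historical median. The only benchmark described mixes the grades 17:11, and that it is the source of Q_S is an inference. If grade is prognostic with a hazard ratio of 1.5 to 3, moving from 61% to 40% or 80% grade II shifts the pooled median of an inert regimen by roughly 1 to 3 months in either direction. These figures rest on the assumed hazard ratios, exponential times and a 10.5-month median at 17:11.

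A reader might go further and infer that the pooled primary estimate should be replaced. The documents do not support that: the weights would come from 28 patients whose link to Q_S is unstated. The stopping probabilities show sensitivity to grade mix; they are not harms that the proposed analysis would remove.

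**What to change.** Keep the pooled posterior of Q_E as the primary estimate, and add the following to Section 8:

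1. State the source of Q_S and the grade mix of the patients behind it.
2. Prespecify a grade-standardised analysis. Fit the same exponential/inverse-gamma model separately to grade II and grade III by central review, and form (17/28)·S_II(t) + (11/28)·S_III(t). If the source of Q_S has another mix, use that mix as the weights.
3. Report the posterior median and 80% interval of that curve beside the pooled posterior and both grade-specific medians, and base the reading against the historical median on both results.
4. Record centrally reviewed grade as an analysis variable.

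No historical grade-specific medians, new patients or new assessments are needed; the change is SAP wording and a few lines of code. The costs are a wider interval when the mixes differ (at HR 2 and 40% grade II, about 8.3 to 13.3 months against 7.4 to 11.4 for the pooled posterior) and some influence of the prior in a sparse grade stratum. The interim stopping rule is unchanged.
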